6.8. Concomitant Therapy

All COPD medications used within 3 months prior to screening and study treatment period (including the post-treatment period) should be recorded in the eCRF.

All non-COPD medications taken during the study (in the treatment phase and up to the safety follow-up contact) and any changes to concomitant medications will be recorded in the eCRF.

The minimum requirement is that the drug name, reason for use, dose (including unit), frequency, route and the dates of administration (start and end dates) are to be recorded.

Note: *Study provided salbutamol should not be recorded in the eCRF however non-study supplied albuterol/salbutamol will be recorded in the eCRF.*

Medications initiated after completion of the treatment phase of the study (Visit 5) or started after discontinuation of study treatment must be recorded in the eCRF up to the safety follow-up contact.

The Medical Monitor should be contacted if there are any questions regarding concomitant or prior therapy.

6.8.1. Permitted Medications and Non-Drug Therapies

6.8.1.1. Permitted COPD Medications

The following COPD medications are permitted during the treatment period:

- Study supplied salbutamol MDI or nebulies (must be withheld for at least 4 hours prior to pulmonary function testing)
- Mucolytics such as acetylcysteine
- Long term oxygen therapy (flow rate of ≤ 3 litres/minute at rest). Oxygen therapy may be adjusted as deemed medically necessary at any time during the treatment phase of the study. Oxygen therapy must be captured on the concomitant medication page of the eCRF. Supplemental oxygen is recommended for participants who exhibit oxyhemoglobin desaturation with rest or exertion (e.g. $\text{SaO}_2 \leq 88\%$)
- Study provided COPD medications in the treatment period
- Any COPD medication deemed medically necessary for the short-term treatment (≤ 14 days) of a moderate/severe COPD exacerbation or pneumonia (such as oral or injectable corticosteroids and/or antibiotics). Any participant that experiences a moderate/severe COPD exacerbation or pneumonia within two weeks prior to screening (in the opinion of the investigator) should be excluded.

6.8.1.2. Permitted Non-COPD Medications

The following non-COPD medications are permitted during the treatment period:

- Medications for rhinitis (e.g. intranasal corticosteroids, antihistamines, cromolyn, nedocromil, nasal decongestants)
- Topical and ophthalmic corticosteroids
- Localized corticosteroid injections (e.g. intra-articular and epidural)
- Vaccinations (Influenza vaccine, Pneumonia vaccine, Shingles vaccine, etc.) (Administration of influenza and pneumonia vaccines should be considered based on clinical discretion of the Investigator and local/national guidelines. Current influenza vaccines and pneumonia vaccines will be captured on the concomitant medication pages of the eCRF)
- Allergy immunotherapy
- Antibiotics for short-term treatment (≤ 14 days) of acute infections. (Long term treatment with antibiotics is not allowed)
- Systemic and ophthalmic beta-blockers. (Administer with caution as systemic beta-blockers block the pulmonary effect of beta-agonists and may produce severe

bronchospasm in participants with reversible obstructive airways disease. Cardio-selective beta-blockers should be considered, although they also should be administered with caution)

- Smoking cessation treatments
- Cough suppressants
- Tricyclic antidepressants and monoamine oxidase inhibitors (MAOIs). (Administer with extreme caution as they may potentiate the effects of beta-agonists on the cardiovascular system, including QT interval corrected for heart rate [QTc] prolongation)
- Diuretics. (Caution is advised in the co-administration of beta-agonists with non-potassium sparing diuretics as this may result in ECG changes and/or hypokalemia)
- Use of positive airway pressure for sleep apnea
- Oral muscarinic antagonists for the treatment of overactive bladder are permitted but should be used with caution as they may exacerbate medical conditions that are contraindicated for anticholinergics (e.g., narrow angle glaucoma and bladder outflow obstruction)
- Cytochrome P450 (CYP)3A4 inhibitors. (Caution should be exercised when considering the coadministration of long-term ketoconazole and other known strong CYP3A4 inhibitors (e.g., ritonavir, clarithromycin, conivaptan, indinavir, itraconazole, lopinavir, nefazodone, neflifavir, saquinavir, telithromycin, troleandomycin, voriconazole) because increased systemic corticosteroid and increased cardiovascular adverse effects may occur)

6.8.2. Prohibited Medications and Non-Drug Therapies

Use of the medications listed in [Table 3](#) is not permitted during the study.

Table 3 Concomitant Prohibited Medications

Medications Prohibited during the treatment period
Inhaled short-acting anticholinergics
Inhaled short-acting beta ₂ agonists ¹
Inhaled short-acting anticholinergic/short-acting beta2-agonist combination products
Inhaled corticosteroids (ICS)
Inhaled corticosteroids (ICS)/Inhaled long-acting beta2-agonist (LABA) combinations (eg. fluticasone/salmeterol, mometasone furoate/formoterol fumarate, budesonide/formoterol fumarate; fluticasone furoate/vilanterol
Phosphodiesterase 4 (PDE4) inhibitors (roflumilast)
LABA (e.g., indacaterol, olodaterol, salmeterol etc.)
Other LAMAs (aclidinium, glycopyrronium, umeclidinium etc.)
LAMA/LABA combinations
Theophyllines
Sodium cromoglycate and nedocromil sodium
Anti-leukotrienes
Long term antibiotic therapy ²
Systemic, oral, parenteral corticosteroids ³
Any other investigational drug

1. (rescue salbutamol will be provided and is permitted during the study)
2. (Antibiotics are allowed for the short-term treatment (≤ 14 days) of an exacerbation or for short term treatment (≤ 14 days) of other acute infections during the study)
3. (During the study oral/systemic corticosteroids may be used for ≤ 14 days to treat COPD exacerbations/pneumonia)

Intra-articular injections are allowed

Note: *Topical and ophthalmic corticosteroids, and localized corticosteroid injections (intra-articular and epidural) are allowed.*

NOTE: *All COPD medications (except for rescue salbutamol, mucolytics and oxygen) are prohibited during the study treatment period, except during the treatment of a moderate/severe COPD exacerbation or pneumonia. In the event of an exacerbation or*

pneumonia, sites should attempt to follow protocol treatment guidelines, however, treatment with any medication that the health care provider deems necessary is allowed. Caution is advised in using a LABA or LAMA to treat a participant currently taking study treatment as these additional medications may increase the risk of overdose. If necessary, the Investigator or other health care personnel may stop the participant's study treatment temporarily (≤ 14 days) in order to treat the COPD exacerbation. Participants who require more than two consecutive 14 day courses of treatment (i.e. antibiotics or corticosteroids) should be evaluated for their continuation on study treatment by the Investigator in consultation with the GSK medical monitor.

The Medical Monitor should be contacted if there are any questions regarding concomitant or prior therapy.

6.8.3. Rescue Medicine

The study site will supply salbutamol rescue medication that will be provided locally.

Although the use of rescue medications is allowable at any time during the study, rescue medication should be withheld for at least 4h hour prior to all pulmonary function tests. Sites should not perform spirometry on subjects who have taken a SABA/salbutamol within 4 hours prior to pulmonary function tests. The subjects will need to wait at the site, or be rescheduled for the next day, whichever is feasible

7. DISCONTINUATION OF FF/UMEC/VI AND PARTICIPANT DISCONTINUATION/WITHDRAWAL

7.1. Discontinuation of FF/UMEC/VI

Participants have the right to discontinue FF/UMEC/VI before the end of the study. A participant may also be asked to discontinue FF/UMEC/VI at the Investigator's discretion.

Participants that permanently stop FF/UMEC/VI should return to the clinic as soon as possible, in order to complete the Treatment Discontinuation visit. The evaluations and procedures to be completed are outlined in the SoA (Section 1.3)

Participants that discontinue FF/UMEC/VI are encouraged to remain in the study and every effort should be made by the Investigator/staff to keep the participant in the study, to collect important efficacy and safety data.

If possible, participants should return to the clinic to complete all scheduled visits. If this isn't possible, visits should be completed by telephone. Ideally, participants should return to the clinic to complete Visit 5, to collect important spirometry data, however, if this isn't possible, this visit could be completed by telephone. A safety follow-up phone call (Visit 6) should also be conducted 7 days after Visit 5.

Following discontinuation of study intervention, if participants are unwilling to return to the clinic for their scheduled visits, the Investigator/site staff should contact the participant by telephone at the protocol designated visit time intervals to collect the following:

- SAEs
- AEs assessed as related to study participation
- AEs resulting in discontinuation of study intervention or withdrawal from the study
- COPD exacerbations
- Concomitant medication
- A safety follow-up phone call (Visit 6) should also be conducted 7 days after Visit 5.

A participant may be withdrawn from study intervention at any time. A reason for premature discontinuation of study intervention (e.g., AE, lack of efficacy, protocol deviation, Investigator discretion, consent withdrawn etc.) must be captured in the eCRF.

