1.2. Schema

1.3. Schedule of Activities (SoA)

Protocol Activity	Pre-Screen	Screen	Treatment					Follow-up
	Visit 0	Visit 1 Screen	Visit 2	Visit 3	Visit 4 ^e (Telephon ic)	Visit 5	Study treatment discontinuation	Safety Follow-up Visit 6 ^f
Study Day			Week 0/Day 1	Week 4/Day 28	Week 12/Day 84	Week 12/Day 85		1-week Follow-up/Day 92
Window		(Day -1)		-4/+2d (Day 24 to 30)	-4/+2d (Day 80 to 86)	-4/+2d (Day 81 to 87)		-1/+4d (Day 91 to 96)
Written Informed Consent ^a	X	X						
Demography ^b	X	X						
Medical History, including cardiovascular history		X						
COPD and Exacerbation History		X						
Concomitant Medication Assessment	X	X	X	X		X	X	X
Inclusion/Exclusion Criteria		X	X					
COVID-19 test ^c		X						
Smoking History		X						
Smoking status		X				X	X	
Smoking Cessation Counselling		X				X	X	
CAT		X						
Baseline/Trough Spirometry ^d			X	X		X		
Exacerbation Assessment			X	X		X	X	X
Physical examination ^g		X				X	X	
Adverse Events Assessment		X	X	X		X	X	X
Vital signs ^h		X				X	X	
ECG		X						
Chest X-ray ⁱ		X						
Oropharyngeal examination		X				X	X	
Urine Pregnancy Test ^j		X				X	X	
Dispense study treatment			X	X				
Administer study treatment ^k			X	X	X			
Assess current COPD treatment compliance			X					

Protocol Activity	Pre-Screen	Screen	Treatment						Follow-up
			Visit 0	Visit 1 Screen	Visit 2	Visit 3	Visit 4 ^e (Telephon ic)	Visit 5	
Study Day				Week 0/Day 1	Week 4/Day 28	Week 12/Day 84	Week 12/Day 85		1-week Follow-up/Day 92
Window		(Day -1)			-4/+2d (Day 24 to 30)	-4/+2d (Day 80 to 86)	-4/+2d (Day 81 to 87)		-1/+4d (Day 91 to 96)
Assess study treatment compliance					X			X	X
Collect study treatment								X	X
Dispense salbutamol as required		X	X	X				X	
Collect salbutamol								X	X
Dispense paper Medical Problems worksheet		X	X	X				X	
Review paper Medical Problems worksheet			X	X				X	X

- a. Informed consent must be conducted prior to performing any study procedures including the changing or withholding of medications. The informed consent may be given at Screening Visit 1 if the participant does not take or has not taken any protocol excluded medications. The Pre-screen and Screening Visits can occur on the same day.
- b. Demography may be captured at either the Pre-screen Visit or Screening Visit (for participants who do not have a Pre-screen Visit).
- c. The test should be done at Visit 1, using a molecular (PCR [polymerase chain reaction] or antigen test) approved by the country regulatory authorities.

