8.3. Adverse Events (AEs), Serious Adverse Events (SAEs) and Other Safety Reporting

The definitions of adverse events (AE) or serious adverse events (SAEs) can be found in Section [10.6](#).

AEs will be reported by the participant (or, when appropriate, by a caregiver, surrogate, or the participant's legally authorized representative).

The investigator and any qualified designees are responsible for detecting, documenting, and reporting events that meet the definition of an AE or SAE and remain responsible for following up AEs that are serious, considered related to the study intervention or the study, or that caused the participant to discontinue the study intervention or study (see Section [7](#)).

The method of recording, evaluating, and assessing causality of AEs and SAEs and the procedures for completing and transmitting SAE reports are provided in [Appendix 6](#).

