8.3.1. Time Period and Frequency for Collecting AE and SAE Information

- All AEs and SAEs will be collected from the start of intervention (Visit 2) until the follow-up contact (Visit 6) at the time points specified in the SoA (Section [1.3](#)). However, any SAEs assessed as related to study participation (e.g., protocol-mandated procedures, invasive tests, or change in existing therapy) or related to a GSK product will be recorded from the time a participant consents to participate in the study.
- Medical occurrences that begin before the start of study intervention but after obtaining informed consent will be recorded as Medical History/Current Medical Conditions not as AEs.
- All SAEs will be recorded and reported to the sponsor or designee, Health Authorities and EC, immediately and under no circumstance should this exceed 24 hours, as indicated in [Appendix 3](#). The investigator will submit any updated SAE data (Follow up report) to the sponsor within 24 hours of it being available and awareness of the same.

Investigators are not obligated to actively seek information on AEs or SAEs after the conclusion of the study participation. However, if the investigator learns of any SAE, including a death, at any time after a participant has been discharged from the study, and he/she considers the event to be reasonably related to the study intervention or study participation, the investigator must promptly notify the sponsor within the timelines mentioned above.

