9.3.2. Safety Analysis

All safety analyses will be performed on the ITT Population.

The primary Estimand is defined by the following:

- Endpoint: AE, SAE and AESI.
- Summary measure:
 - number and percentage of participants experiencing an AE
 - number and percentage of participants experiencing a SAE
 - number and percentage of patients experiencing an AESI
- Population of interest: COPD patients in India.
- Key intercurrent events: discontinuation of treatment
- Strategy for intercurrent events: a While on Treatment strategy will be used for treatment discontinuation. This estimates the percentage of participants experiencing an AE, SAE or AESI while taking treatment.
- Participants that test positive for COVID-19 will immediately discontinue study treatment. Therefore COVID-19 will be included as the intercurrent event of study treatment discontinuation and will be handled with While on Treatment strategy for the primary estimand.

A supplementary estimand will be defined using identical properties as for the primary estimand (summary measure, population of interest and key intercurrent events), however

this supplementary estimand will report all AEs regardless of the discontinuation of study treatment.

- Endpoints: Incidence of AEs, SAEs and AESIs
- Strategy for intercurrent events: Treatment policy strategy will be used for treatment discontinuation. This summary will therefore be inclusive of all on-treatment and post-treatment AEs.

In addition, summary statistics for vital signs and their change from baseline at Day 85: heart rate, systolic blood pressure and diastolic blood pressure will be produced.

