- Study participants in the treatment phase of the study (Visit 2 to Visit 5) should be contacted by sites at each scheduled study visit to collect the following:
 - SAEs

- AEs
- COPD exacerbations
- Concomitant medication
- Compliance with study intervention
- **Note:** *The secondary objective of the study is to evaluate the effect of FF/UME/C/VI on lung function, after 12 weeks of treatment. It will not be possible for study participants to complete spirometry assessments at home, therefore the sample size may need to be increased, to ensure there are a sufficient number of evaluable participants with completed spirometry assessments.*
- For study participants that have completed the treatment phase and have only the safety follow-up visit (Visit 6) to complete, this visit can be completed via the telephone, as specified in the SoA.

Study Intervention(s)

- If allowed by country regulation/ethics, study intervention (including rescue study medication) can be shipped direct-to-patient (DTP) from the investigational site to the participant's home address. The process for this shipment must be agreed with GSK who will provide the relevant documentation and links to courier sites required to ensure shipments are adequately temperature controlled (if required) throughout transportation
- The Principal Investigator assumes Good Clinical Practice (GCP) responsibilities for IMP handling and the medical control for dispensing to patients. Site Staff should document the dispensing in the Dispensing/Accountability Logs adding a comment that this was a DTP dispensing.
- In some cases, trial participants who no longer have access to investigational product or the investigational site may need additional safety monitoring.

Data Management/Monitoring:

- If on-site monitoring is no longer permitted, GSK will consider remote Source Data Verification/Source Document Review (SDV/SDR) where permitted by the clinical site/institution. Remote SDV/SDR will be proposed to study sites to meet a patient and/or critical quality need, e.g., to assess participant safety or to ensure data integrity. In case of remote SDV/SDR, GSK will work with the site to ensure subject privacy.

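### Protocol 7.1's telephone list for discontinued participants who will not return to the clinic omits AEs that 8.3.1, the SoA and the supplementary safety estimand require

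*Protocol*

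**What the plan says.** Protocol 7.1 addresses participants who stop FF/UMEC/VI but stay in the study. It asks them to attend a Treatment Discontinuation visit and the remaining scheduled visits, by telephone where attendance is not possible. It then adds a separate instruction: "if participants are unwilling to return to the clinic for their scheduled visits", staff should telephone at the visit times and collect a stated list. The AE items on that list are SAEs, "AEs assessed as related to study participation", and AEs that caused discontinuation or withdrawal. COPD exacerbations and concomitant medication are also listed, together with the Visit 6 call.

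Other passages set no such filter:

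- Protocol 8.3.1: "All AEs and SAEs will be collected from the start of intervention (Visit 2) until the follow-up contact (Visit 6"), with no exception after discontinuation.
- Protocol 1.3 (SoA): the row "Adverse Events Assessment" is marked at Visits 3, 5 and 6 and at the treatment discontinuation visit.
- Protocol Appendix 4, for COVID-19 disruption: participants in the treatment phase "should be contacted by sites at each scheduled study visit to collect the following", and the list that follows names AEs without qualification.
- Protocol 8.3: investigators "are responsible for detecting, documenting, and reporting events that meet the definition of an AE or SAE". Separately, they "remain responsible for following up AEs that are serious, considered related to the study intervention or the study", or that led to discontinuation.

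For the supplementary safety estimand, Protocol 9.3.2 states: "This summary will therefore be inclusive of all on-treatment and post-treatment AEs". SAP 17.1.2 notes that a treatment-policy strategy needs data collected after the intercurrent event, and it sends the supplementary analysis to SAP section 14. SAP 14.1 counts participants with a post-treatment AE. The SAP does not mention the shorter list.

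**The concern.** The 7.1 list resembles the follow-up duty in 8.3, which is limited to serious, related or discontinuation-causing events. Section 7.1 applies that kind of filter to collection, whereas 8.3 requires every AE to be detected and documented. Two sites could each point to the protocol and record different data for the same kind of participant. Whether a non-serious AE is recorded after discontinuation would then depend on the site's reading and on an open-label causality judgement.

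The affected participants are among those the supplementary estimand was added to cover. If the list is followed as written, that summary cannot be described as containing all post-treatment AEs.

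**Working it through.** **Comparing the passages.** Take a non-serious AE that starts after treatment has stopped, is judged unrelated to study participation and did not cause the discontinuation.

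| Passage | Is the event collected? |
|---|---|
| Protocol 7.1 short list | Not listed |
| Protocol 8.3.1 | Yes, up to Visit 6 |
| SoA, Visits 3, 5 and 6 | Yes |
| Protocol 8.3, detection and documentation | Yes |
| Supplementary estimand, 9.3.2 and SAP 17.1 | Assumed to be in the data |

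The gap may be wider if 7.1 is read literally. In setting the rule for SAEs, 8.3.1 distinguishes events related to study participation (procedures, tests, change of existing therapy) from events related to a GSK product. On that usage, a non-serious drug-related AE that did not cause discontinuation is also off the 7.1 list.

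**Where the gap closes.** The short list affects the calls that replace Visits 3 and 5. The SoA has a full AE assessment at Visit 6. Protocol 8.2.3 (pneumonia), 8.2.8 (positive COVID-19 tests) and 8.3.5 (AESI notification) have their own reporting rules. The AESI route helps only when the site learns of the event, because SAP 17.1.1 derives AESIs from a question on recorded AEs. Participants who stopped because of an AE or a positive COVID-19 test already count in any-AE incidence, so for them only SOC or PT rows can be short.

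**Size.** Inputs from Protocol 9.2 are 229 enrolled, 220 evaluable and 4% withdrawal from study treatment.

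- Check on the plan's figures: 220 / (1 - 0.04) = 229.2, against 229 stated; 4% of 229 = 9.16.
- Discontinuers: 229 - 220 = 9.
- Cap, if all 9 are followed by the short list and each has an unlisted AE as the only AE: 9 / 229 = 3.93 percentage points.
- One missed participant in a SOC or PT row: 1 / 229 = 0.44 points.

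A narrower range needs three assumptions that the documents do not supply: 25% to 100% of the 9 are followed by the short list; 10% to 50% of those have an unlisted AE and no other counted AE; Visit 6 recovers 0% to 50% of these.

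- Low: 9 × 0.25 × 0.10 × (1 - 0.50) = 0.11 participants; 0.11 / 229 = 0.05 points.
- High: 9 × 1.00 × 0.50 × (1 - 0) = 4.5 participants; 4.5 / 229 = 1.97 points.

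The cap scales with discontinuation. If 10% stopped (23 of 229, also an assumption), it would be 23 / 229 = 10.0 points.

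**The case against.** The strongest reply is that the passages can be reconciled. Section 7.1 does not say that only the listed items are to be collected, so it can be read as a minimum with 8.3.1 as the governing rule. A site must hear of an AE before judging whether it is related, and 8.3 already obliges it to document what it hears. The list also reaches few people: discontinuers who attend, or whose visits move to the telephone because attendance is not possible, meet no filter. Appendix 4 concerns COVID-19 disruption and is not a rule for people who decline visits.

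Most of this stands, and it is why the point is minor. A site that collects everything complies with all the passages and loses nothing. If Visit 6 recovers every event, the shortfall is also zero, so the low figure of 0.05 points reflects the assumed 50% limit on recovery and is not a floor. Appendix 4 shows only that the protocol regards full AE collection by telephone as workable. Some of the 9 may leave the study altogether, in which case no call list applies.

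The objection does not remove the difference itself. Section 7.1 gives an explicit list for a defined group, and a site that follows it collects less than 8.3.1 requires and less than the estimand claims. Recovery at Visit 6 relies on later recall. Section 7.1 also places that call in the same list without saying whether the filter applies to it.

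**Conclusion.** The inconsistency is real and minor. Section 7.1 is narrower than 8.3.1 and the SoA, and narrower than the supplementary estimand that depends on these data. The effect is confined to a descriptive supplementary summary in a single-arm study with no hypothesis tests. The primary estimand could be touched only through on-treatment AEs not yet reported when a participant skips the discontinuation visit.

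The 3.9-point cap holds at the planned 4% discontinuation, and the true effect is probably well below it. The 0.05 to 2.0 point range depends wholly on the three stated assumptions. No design figure changes.

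**What to change.** In Protocol 7.1, replace the three AE items in the telephone list with a single item covering all AEs and SAEs, so that it agrees with 8.3.1, the SoA and Appendix 4. No treatment rule changes.

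Under Protocol 10.1.1 this is an amendment needing ethics committee approval before implementation, plus health authority approval if judged substantial. The calls and the AE eCRF page already exist, so the running cost is slightly longer calls.

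The documents do not show how far the study has progressed. If the short list has already been used, qualify the statement that the supplementary summary includes all on-treatment and post-treatment AEs, in the SAP or the study report. Also report how many participants were followed by the short list. That count is possible only if the mode of follow-up can be read from the eCRF or site records.
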